Patient-centered care as it relates to patient preference and satisfaction has become one of the major goals in healthcare reform and transformation. Patient centeredness is a dimension of health care quality because of its connection with desired aims, like safety and effectiveness. Patient centeredness and satisfaction shifts the control from the hands of those who give care into the hands of those who receive it. Patient satisfaction with healthcare medications has been shown to affect treatment-related behaviors such has their likelihood of complying and continuing to use their medication correctly. ¹⁶Thus, patient satisfaction translates into improved patient-centered outcomes and quality of care. The basis for this assessment will be overall patient medication satisfaction/preference at the end of week 3 and 6. More descriptive data (effectiveness, convenience and global satisfaction) relating to a patient's choice will be measured as a secondary outcome by the reliable and validated TSQM-9 tool.

Standard practice within the PRTBTC for prophylactically preventing nausea and vomiting associated with chemoradiation is the administration of ondansetron. With the administration of ondansetron orally 1-3

times a day for multiple days, compliance is a problem within this patient population. Newer approaches to treatment such as a single dose rolapitant should have fewer or minimal compliance problems. Hence, there is interest in understanding patient efficacy and preference relative to ondansetron. Compliance of ondansetron vs. rolapitant and ondansetron is also of interest.

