| Secondary | Evaluate patient compliance with rolapitant plus ondansetron and ondansetron monotherapy | The compliance rate defined as the percentage of days that rolapitant plus ondansetron or ondansetron alone were used during the six weeks | See section 15.5.2 |
| Secondary | Assess the safety of rolapitant plus ondansetron in the prevention of RINV in primary glioma patients receiving RT and concomitant TMZ | The percentage of patients experiencing a grade ≥3 treatment-related toxicity. Toxicity (adverse events) will be assessed throughout the 6-week treatment period. This data will be collected via NCI Common Toxicity Criteria (CTC) (vs 4) | See section 15.5.2 |

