10.7.3 Dosage and Administration

Ondansetron will be administered on both arms of the protocol at 8 mg p.o, daily on Days 1- 42 days, 30-60 minutes prior to each dose of chemotherapy. A prescription for Ondansetron 8 mg p.o. daily 30-60 minutes before temozolomide X 7 days (with 6 refills) will be provided by provider.

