15.5.2 Other Secondary Objectives

Mean patient satisfaction scores for effectiveness, convenience and global satisfaction, will be computed based upon responses to the TSQM-9 treatment satisfaction survey¹⁶ that patients complete at the end of week 3 after treatment with ondansetron alone or combination treatment. Three subscales will be computed: effectiveness (3 items), convenience (3 items), and global satisfaction (3 items). Assuming there is no evidence of a carry-over effect, a paired t-test will be conducted comparing satisfaction with combination treatment and with ondansetron treatment alone.

The efficacy of rolapitant plus ondansetron vs. ondansetron monotherapy in the prevention of nausea and vomiting will be separately assessed, as measured by the respective CIN, CIV CR rates, among malignant glioma patients during RT and concomitant TMZ. The CR outcome for nausea will be defined as no use of rescue medication for nausea, while the CR outcome for vomiting will be defined as no use of rescue medication for vomiting. The CIN and CIV CR rates will be assessed via the modified MASCC Antiemesis Tool (MAT).

For each 3-week treatment regimen, compliance is defined as the percentage of days that pills were appropriately used. The distribution of compliance during treatment with ondansetron alone and with combination treatment will be described with a frequency distribution. A nonparametric paired test (e.g. Wilcoxon) may be used to compare compliance within the two regimens (as documented on the medication logs).

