15.7 Sample Size Calculation

15.7.1 Original Study Design

One hundred seventy (170) glioma patients will be enrolled with the expectation that 160 patients will be randomized to receive one of two treatment sequences of anti-emetic therapy for the prevention of nausea and vomiting associated with RT and concomitant TMZ. A permutated block randomization with an allocation ratio of 1:1 will be used to assign patients to sequence A or B. Sequence A involves a 3-week regimen of daily ondansetron followed by a 3-week regimen consisting of rolapitant (day 22 only) and daily ondansetron; whereas Sequence B involves a 3-week regimen of rolapitant (day 1 only) and daily ondansetron followed by a 3-week regimen of daily ondansetron. The study has one primary and one KEY secondary endpoint: CR rate and patient overall preference for ondansetron treatment with or without rolapitant. Though the primary CR rate endpoint will focus on treatment during the first 2 weeks of RT and TMZ, a crossover design is proposed so that a patient will experience both modes of treatment, and be equipped to make a comparative assessment of preference.

Power Calculations for Complete Response, Primary Endpoint: The power of the comparison of ondansetron and the combination of ondansetron and rolapitant relative to the CR rate during the initial 2 weeks of treatment with RT and TMZ will be considered here. This comparison will focus on the anti-emetic experience during the first regimen of the two treatment regimens that the patient will receive. Let

p₁ = overall complete response rate for the first 2 weeks of treatment with the combination antiemetic regimen, and

 p_0 = overall complete response rate during the first 2 weeks of treatment with ondansetron alone.

The hypothesis that will be assessed is whether the CR rate with combination treatment is greater than that with ondansetron alone. Specifically, the hypothesis that will be tested is as follows:

 H_0 : $p_1 \le p_0$ versus H1: $p_1 > p_0$

Temozolomide prescribing information reports a vomiting rate of 20% with concomitant RT + TMZ. Anti-emetic treatment failure includes the occurrence of vomiting or the use of an anti-emetic for nausea and/or vomiting. Therefore, we anticipate that approximately 25% of patients receiving ondansetron alone to either vomit or receive an anti-emetic. Equivalently, a CR rate of 75% is anticipated with ondansetron alone.

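### The days-based compliance score in Section 15.5.2 mostly measures daily ondansetron and is insensitive to a missed rolapitant dose

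*Combined protocol and SAP*

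**What the plan says.** The analysis rule is in Section 15.5.2. It opens with "For each 3-week treatment regimen" and continues: "compliance is defined as the percentage of days that pills were appropriately used". The score is to be described by a frequency distribution, and then "A nonparametric paired test (e.g. Wilcoxon) may be used to compare compliance within the two regimens".

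The endpoint table in Section 8 words the measure differently: "The compliance rate defined as the percentage of days that rolapitant plus ondansetron or ondansetron alone were used during the six weeks".

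The schedule is set out in Sections 15.7.1 and 10.7.3. For one sequence, "Sequence B involves a 3-week regimen of rolapitant (day 1 only) and daily ondansetron followed by a 3-week regimen of daily ondansetron". For Sequence A, the second period is a "3-week regimen consisting of rolapitant (day 22 only) and daily ondansetron". On the background drug: "Ondansetron will be administered on both arms of the protocol at 8 mg p.o, daily on Days 1- 42 days".

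Section 7.3 gives the reason for the interest in compliance: "Newer approaches to treatment such as a single dose rolapitant should have fewer or minimal compliance problems".

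Two other places bear on the point. Section 9.4.2 has patients log the date and time of both drugs, and lets rescue medication stand in for a missed dose, without saying how such a day is scored. Section 15.3 plans a tabulation, within each sequence, of how many weeks each regimen was received.

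**The concern.** The protocol sets out to evaluate compliance with the combination and with ondansetron alone, and expects a single-dose agent to cause few compliance problems. The drug that distinguishes the regimens is taken on one day. The drug taken on all the other days is the same in both periods. A percentage of days therefore gives the distinguishing drug very little weight.

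Two things are at stake. First, the reported compliance for the combination could look high even if an appreciable share of patients never took rolapitant. Second, no planned analysis reports the proportion who took the dose. Rolapitant is self-administered, and readers will want that proportion when they interpret the efficacy and preference results of a trial reduced to 57 patients.

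**Working it through.** The documents state no compliance rate, effect size or power for this endpoint, so there is no plan figure to reproduce. The check uses the schedule.

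**Inputs.** Window: 3 weeks = 21 days per regimen (Section 15.5.2). Rolapitant: 1 day of 21, day 1 or day 22 (Section 15.7.1). Ondansetron: every day, days 1 to 42, in both regimens (Section 10.7.3).

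**Step 1. Overlap of the regimens.** The required pills are identical on 20 of 21 days: 20/21 = 95.2%.

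**Step 2. One patient misses rolapitant and takes ondansetron every day.**
- If the rolapitant day counts as failed: (21 − 1)/21 = 95.2%.
- If ondansetron alone makes the day count: 21/21 = 100%.
- A patient who took rolapitant but missed ondansetron on one other day: 20/21 = 95.2%.

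Under the first rule the two kinds of lapse give the same score. Under the second, the missed rolapitant dose leaves no trace.

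**Step 3. Effect on the mean.** Let m be the proportion who miss rolapitant and a the probability that ondansetron was taken on that day. If a missed rolapitant dose fails the day, the mean combination score falls by m × a × 1/21. The documents give neither m nor a, so both are assumptions:
- a = 1: m = 10% gives 0.48 points, 20% gives 0.95, 25% gives 1.19, 50% gives 2.38 and 100% gives 4.76.
- a = 0.8: m = 25% gives 0.95 points and 100% gives 3.81.

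A yes/no measure of rolapitant intake would fall by the whole of m, for example by 25 points at m = 25%.

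**Step 4. Sensitivity of the paired test (illustration).** A two-sided 0.05 Wilcoxon signed-rank test was simulated on 57 pairs of 21-day scores, 600 runs per cell. Ondansetron adherence varied between patients but had the same mean in both periods, and a missed rolapitant dose failed its day. The test level and the adherence figures are assumptions; Section 15.5.2 states neither. Percentage of runs rejecting:

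| Mean ondansetron adherence | 0% miss rolapitant | 10% | 25% | 50% | 100% |
|---|---|---|---|---|---|
| 99% | 5.3 | 18.2 | 74.0 | 99.5 | 100 |
| 95% | 5.0 | 7.7 | 27.8 | 75.8 | 100 |
| 90% | 5.2 | 6.5 | 13.3 | 43.7 | 95.8 |
| 80% | 7.5 | 6.2 | 7.8 | 20.8 | 62.8 |

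The Monte Carlo standard error is at most √(0.25/600) = 2.0 points. The simulated mean differences agree with Step 3: at 100% missed they run from −4.72 points (99% adherence) to −3.76 (80%). The test responds to missed rolapitant when ondansetron adherence is nearly perfect or the dose is missed very widely, and otherwise seldom.

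**Step 5. Section 8 against Section 15.5.2.** Section 8 refers to six weeks; Section 15.5.2 scores each three-week regimen. If each regimen's days were divided by 42, a fully compliant patient would reach only 21/42 = 50%. If Section 8 were read as days on which both drugs were taken, a fully compliant patient would score 1/21 = 4.8% for the combination. Neither is a plausible intention, so this is a wording mismatch to be aligned.

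**The case against.** The strongest reply is that the objective concerns regimens. The two regimens share 20 of 21 days by design, and a days-based score reflects that. Section 7.3 locates the compliance problem in repeated daily ondansetron, so whether daily pill-taking differs between periods is a fair question. That stands, and it is why the ondansetron comparison should be kept. It does not justify folding a single-day drug into the same percentage.

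Second, Section 15.3 tabulates weeks of therapy with rolapitant, and on a natural reading a patient who never took it would show none. That stands in part: exposure is not wholly unreported. But a count of weeks is an unclear record of a one-day dose and is not a dose-taken rate with an interval.

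Third, the 95.2% is conditional. It needs ondansetron on all 21 days and a scoring rule that fails the rolapitant day. The text does not define appropriate use, and the medication logs in Appendices 3 and 4 are attachments whose content is not in the available text, so a daily rule may be set there. That stands, and both results are therefore given.

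Fourth, the paired test is optional, the committed analysis is descriptive, and no compliance threshold classifies or excludes anyone. All of this stands and limits the consequence.

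**Conclusion.** The point holds as one of insensitivity. Section 15.5.2's score gives rolapitant a weight of at most 1/21, or 4.8 percentage points. It scores a missed rolapitant dose either the same as one missed ondansetron day (95.2%) or as full compliance (100%). The limit follows from the documents' schedule; the mean shifts and rejection rates rest on assumed miss rates and adherence.

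A reader might infer more than this, and the documents do not support it:
- That the paired test merely compares ondansetron with itself. One day in 21 differs, and the illustration shows the test can respond.
- That the trial would have no way of knowing who took rolapitant. Intake is logged with date and time, and Section 15.3 gives a partial view.
- That Section 8 shrinks the effect of a missed dose to 1/42 = 2.4 points. That needs the strained denominator in Step 5.
- That the main result is compromised. Compliance is a non-key secondary endpoint; the complete response analysis focuses on all randomized patients (Section 15.1), and neither it nor the preference analysis uses this score.

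The change is worth making because it gives a clearer answer from data already planned.

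**What to change.** In Section 15.5.2, replace the single score with two measures taken from the medication log:

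1. The proportion of patients who took the rolapitant dose (yes/no), with a 95% confidence interval. State the denominator, since in Sequence A the dose is not due until day 22. Add timing relative to the first radiation fraction only if the fraction time is recorded; the documents do not say that it is.
2. The percentage of days on which ondansetron was taken in each three-week regimen, described by a frequency distribution and compared within patient.

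Define what counts as a day of appropriate use for this analysis, including how a day made up under Section 9.4.2 is scored. Reword the compliance row in Section 8 so that it uses the three-week, per-regimen denominator.

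The cost is protocol and SAP wording. Dates and times for both drugs are already logged under Section 9.4.2, so no new data collection is needed for the two measures; only the optional timing check depends on an item the documents do not mention.

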5 PROTOCOL SYNOPSIS AND RESEARCH SUMMARY

5.1 Purpose

The purpose of this two-arm randomized phase 2 study is to assess the efficacy and patient satisfaction of oral rolapitant plus ondansetron vs. oral ondansetron *monotherapy* in malignant glioma (MG) patients receiving six weeks of standard cranial radiation therapy (RT) and concomitant temozolomide (TMZ).

Primary Objective:

Compare the efficacy of rolapitant plus ondansetron vs. ondansetron mono therapy in the prevention
of chemoradiation-induced nausea and vomiting (chemo-RINV), as measured by the overall complete
response (CR) rate (where CR is defined as no emesis, no rescue antiemetic), among malignant glioma
patients during the standard ~ 6 weeks of RT and concomitant multi-dose TMZ

Secondary Objectives:

- KEY secondary objective: Assess whether malignant glioma patients receiving RT and concomitant TMZ
 are more satisfied with rolapitant plus ondansetron vs. ondansetron monotherapy for the prevention of
 chemo-RINV
- 2. Describe the rationale behind a patient's satisfaction with antiemetic preference based upon effectiveness, convenience and global satisfaction
- 3. Compare the efficacy of rolapitant plus ondansetron vs. ondansetron monotherapy in the prevention of nausea and vomiting separately, as measured by the respective CIN, CIV -CR rates, among malignant glioma patients during RT and concomitant TMZ
- 4. Evaluate compliance of rolapitant plus ondansetron vs. ondansetron monotherapy
- 5. Assess the safety of rolapitant plus ondansetron vs. ondansetron monotherapy in the prevention of RINV in glioma patients receiving RT and concomitant TMZ

Hypotheses

1. This is a hypothesis-testing protocol. Hypothesis: rolapitant plus ondansetron will produce an equally or a more effective RINV CR rate when compared to ondansetron monotherapy in glioma patients receiving RT and concomitant TMZ.

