9.6 Randomization

A permuted block randomization will be used to assign patients, in an unblinded fashion, to one of two treatment sequences as described in Section 9.1. A 1:1 allocation ratio will be used.

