12 SCREENING AND ON-STUDY TESTS AND PROCEDURES

Patients will be initially screened during the -28 to 0 days prior to study initiation. During this time period, the following will be recorded: physical examination; vital signs and weight; laboratory studies (complete blood count with differential, platelet, blood chemistries, liver function tests and urinalysis); past medical history; concomitant medications (steroids and anticonvulsants); and predictors of RINV (e.g. irradiation site, planned dose, treatment field, alcohol intake, gender, age). Prior to study enrollment, patient's medications should be reviewed by the clinical pharmacist to prevent concerns with drug interactions. The patient's medications will be evaluated by the PI, the patient's study physician, and/or the study pharmacist on a case by case basis for safety. Laboratory evaluations, performance status, concomitant medications, and adverse events for final eligibility should be confirmed within 2 weeks of initiating radiation with concomitant TMZ.

Patients will be filling out data collection tools (i.e. MAT and TSMQ-9) day 0 (baseline) and days 1, 2, 4, and 7 (for days 7, 1, 2-3, and 4-6, respectively) of each week of radiation therapy. In addition, they will be recording their medication and the use of rescue medication in a medication log as noted below (See Section 12.7 and appendices for study tools).

The CRC will be collecting data from the tools listed below and placing data in an electronic database that is 21CFR Part 11 compliant (e.g. Medidata Rave). Monthly meetings between the CRC and primary investigators will occur to review data. Patient Surveys and follow up phone calls will be conducted weekly to obtain and validate data. The CRC is required to monitor protocol patients weekly or as many times as necessary to obtain toxicities. Toxicities are obtained via clinical notes or telephone conversations with the local oncology office and/or patient. The National Cancer Institute (NCI) Common Toxicity Criteria (CTC) Version 4 is to be used to score the adverse advents. All graded toxicities are then entered in the database and reviewed together with the Primary Investigator (PI) and CRC and confirmed by source documents. Attributions are approved by primary investigators.

Table 7: Screening and Study-related Tests and Procedures

| Phase | Screen | Start | Study Period | | | End | |

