13.1 Adverse Events

An adverse event (AE) is any untoward medical occurrence in a subject receiving study drug and which does not necessarily have a causal relationship with this treatment. For this protocol, the definition of AE also includes worsening of any pre-existing medical condition and the onset of new illness. An AE can therefore be any unfavorable and unintended or worsening sign (including an abnormal laboratory finding), symptom, or disease temporally associated with the use of rolapitant plus ondansetron vs ondansetron alone whether or not related to use of the rolapitant plus ondansetron vs ondansetron alone. But laboratory value changes that require therapy or adjustment in prior therapy are considered adverse events.

From the time the subject signs the informed consent form through the End of Study visit (as defined in Section 12.5), all AEs must be recorded in the subject medical record and adverse events case report form.

AEs will be assessed according to the CTCAE version 4. If CTCAE grading does not exist for an AE, the severity of the AE will be graded as mild (1), moderate (2), severe (3), life-threatening (4), or fatal (5).

Attribution of AEs will be indicated as follows:

- Definite: The AE is clearly related to the study drug
- Probably: The AE is likely related to the study drug
- Possible: The AE may be related to the study drug
- Unlikely: The AE is doubtfully related to the study drug
- Unrelated: The AE is clearly NOT related to the study drug

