For the manuscript, adverse events that are possibly, probably, and definitely treatment related that are reported during the ~ 6 weeks of treatment will be summarized. For each type of adverse event experienced by a patient during rolapitant plus ondansetron and during ondansetron treatment, the maximum grade experienced by each patient will be tabulated by treatment group (i.e. rolapitant plus ondansetron or ondansetron treatment). Given the cross-over design of this study, patients will contribute data to both treatment groups. Two tabulations of toxicity data will be generated for review by the Safety Oversight Committee including one that includes all toxicities regardless of attribution, and another that includes only toxicities that are possibly, probably, and definitely related to protocol treatment. For each of these tabulations, the maximum grade of each type of toxicity experienced by each patient will be summarized with frequency distributions within each treatment (rolapitant plus ondansetron vs. ondansetron). For ClinicalTrials.gov, serious adverse events and other adverse events will be summarized separately. These tabulations will reflect the number of patients who experience each type of toxicity regardless of grade or attribution.

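### The safety endpoint and manuscript summary count only events that unblinded investigators judge treatment-related; add the all-cause grade ≥3 figure by regimen beside them

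*Combined protocol and SAP*

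**What the plan says.** Section 5.1 states the safety objective as a comparison: "Assess the safety of rolapitant plus ondansetron vs. ondansetron monotherapy in the prevention of RINV". Section 8 gives the endpoint: "The percentage of patients experiencing a grade ≥3 treatment-related toxicity". Section 15.5.2 describes three outputs:

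- **Manuscript.** The summary opens "For the manuscript, adverse events that are possibly, probably, and definitely treatment related", covers the roughly six weeks of treatment, and tabulates each patient's maximum grade for each event type by regimen.
- **Safety Oversight Committee.** Two tables of maximum grade per event type within each regimen, one covering all toxicities whatever their attribution and one limited to related toxicities.
- **Registry.** Serious and other adverse events are summarised separately, as numbers of patients per event type without regard to grade or attribution. A split by regimen is not stated.

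On who judges relatedness, Section 9.6 says "A permuted block randomization will be used to assign patients, in an unblinded fashion, to one of two treatment sequences", and Section 12 says "Attributions are approved by primary investigators". The scale in Section 13.1 has five levels, from "Definite: The AE is clearly related to the study drug" down to unrelated, and includes "Possible: The AE may be related to the study drug". No blinded or independent adjudication is described. Section 13.1 also requires that "all AEs must be recorded in the subject medical record and adverse events case report form", and Section 12 has all graded toxicities entered in the database.

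**The concern.** To enter the Section 8 endpoint or the manuscript table, an event must first be called at least possibly related by someone who knows which regimen the patient is on. That judgement has little to anchor it here. Section 5.8 lists headache, fatigue and constipation as the commonest ondansetron effects. Section 5.2 names the same three as the most frequent treatment-related events in the phase 3 rolapitant trial in moderately emetogenic chemotherapy. Section 9.3.4 lists fatigue and headache among radiation effects. Where causes overlap this much, knowing the regimen can tip the call.

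What is at stake is how a reader of the manuscript judges the safety of adding rolapitant. A difference between regimens, or the lack of one, could partly reflect attribution habit. The graded data that avoid this step are collected, and even tabulated by regimen, but that table is not assigned to the manuscript.

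**Working it through.** The plan gives no expected adverse event rate, test, margin or alpha for safety, so there is no stated figure to reproduce. The check has three parts.

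**1. The outputs side by side.**

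| Output | Attribution | Grade shown | By regimen |
|---|---|---|---|
| Section 8 endpoint | related only | ≥3 | implied by the Section 5.1 objective |
| Manuscript table (15.5.2) | related only | maximum grade per event type | yes |
| Committee table 1 (15.5.2) | all | maximum grade per event type | yes |
| Committee table 2 (15.5.2) | related only | maximum grade per event type | yes |
| Registry tables (15.5.2) | all | none | not stated |

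Only the first committee table is all-cause, graded and by regimen. Neither the endpoint nor the manuscript has a figure with all three properties.

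**2. How far attribution alone could move the endpoint.** All inputs here are assumptions. Let q be the percentage of patients with a grade ≥3 event of any cause, equal in both regimens, and let a be the chance that the event is called related. Treating each such patient as having one event, the related rate is q × a. The ratio between regimens is then a(combination) ÷ a(ondansetron), whatever q is. Take a = 30% on ondansetron alone:

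| q | ondansetron, a = 30% | combination, a = 40% | a = 50% | a = 60% |
|---|---|---|---|---|
| 10% | 3% | 4% | 5% | 6% |
| 20% | 6% | 8% | 10% | 12% |
| 40% | 12% | 16% | 20% | 24% |
| ratio | | 1.33 | 1.67 | 2.00 |

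With equal attribution the ratio is 1.00. If the habit runs the other way, the ratios invert: 30/40 = 0.75, 30/50 = 0.60, 30/60 = 0.50.

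In patients: the accrual target is 57 (Section 15.4), and with the crossover each regimen has at most 57. One patient is 1/57 = 1.75 percentage points. At q = 20%, a spurious difference of 2 to 6 points is 0.02 × 57 = 1.1 to 0.06 × 57 = 3.4 patients. For scale, Section 9.2 cites 7% grade 3/4 fatigue with radiation and temozolomide, and 0.07 × 57 = 4.0 patients. That 7% is not a rate per three-week regimen, so it shows only that counts are likely to be small.

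**3. Whether the committee table yields the missing figure.** It records maximum grade separately for each event type. A patient with grade 3 events of two types appears in two rows. The number of patients with any grade ≥3 event is therefore at least the largest row and at most the sum of the rows, and cannot be read off. It needs a patient-level derivation. The Section 8 endpoint, also a percentage of patients, needs the same derivation with the attribution filter left on.

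**The case against.** The strongest reply is that safety is not assessed on attributed events alone. That is right. A reader of Section 8 might infer that the whole between-regimen comparison rests on relatedness calls, but 15.5.2 gives the committee an all-cause, graded, by-regimen table and sends all-attribution tables to the registry. It also does not bar publishing the committee table. The gap is one of assignment: that table belongs to neither the endpoint nor the manuscript.

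A reader might also infer that open-label attribution will make the combination look worse. The documents support neither that direction nor any size. Section 12 has graded toxicities reviewed by the principal investigator and coordinator and confirmed by source documents. That is a check on the record, though not blinded adjudication.

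A third tempting reading is that events in Sequence A weeks 1–3 have no study drug to be related to, since Sections 5.8 and 5.9 use the term for rolapitant. But Section 10.7 lists ondansetron among the study drugs, and the adverse event definition in 13.1 covers both regimens. Having two candidate drugs on the combination is a real difference in exposure, not bias in itself.

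Three further points stand. Sections 8 and 15.5 word the safety objective without a comparator, and 15.5.2 specifies frequency tables with no test, so the plan defines no formal safety conclusion that could be overturned. All-cause rates will carry radiation, temozolomide and tumour effects, which may dilute a drug signal. Reporting related events in a manuscript is a defensible choice, which argues for adding the all-cause figure rather than replacing the related one.

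**Conclusion.** The point holds in a limited form. The endpoint and the manuscript's by-regimen summary both pass through a relatedness judgement made with knowledge of the regimen, while the all-cause, graded, by-regimen table goes only to the committee. The manuscript comparison is therefore open to differential attribution of unknown direction and size, on a secondary endpoint analysed descriptively. The ratios of 1.33 to 2.00, or 0.75 to 0.50 in reverse, show what is possible under the assumed attribution chances; they do not estimate a likely bias. An all-cause figure removes the attribution step only. Open-label influence on which events are reported, and how they are graded, remains.

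**What to change.** In Section 8, add to the safety endpoint the percentage of patients with at least one grade ≥3 adverse event regardless of attribution, by regimen. In Section 15.5.2, assign that figure to the manuscript together with the all-cause maximum-grade table already planned for the Safety Oversight Committee, and report the treatment-related figures alongside.

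The cost is wording in two sections and one patient-level derivation from data already collected; no new visits, patients or data items are needed. The manuscript should say that the all-cause percentages include radiation, temozolomide and tumour effects and may dilute a drug signal, and that reporting and grading were open label.
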